## **4.2 Intervention**

The T-cells to be infused will be selected based on criteria mentioned in section 4.0 from our bank of GMP grade adimleculecel. T-cells will be administered by bolus intravenous infusion. In this phase II trial, patients will be treated at doses of  $1 \times 10^6$  adimleculecel /kg/dose/week (with an acceptable range of  $0.8 - 1.2 \times 10^6$  cells/kg) for 3 weeks or total dosing of  $2.4 - 3.6 \times 10^6$  cell/kg per cycle. Patients

will be observed for the following 3 weeks. Additional 3 week courses of adimlecleucel may be administered if levels of CMV DNA in blood are still detectable despite disease stabilization or improvement.

The rationale for the doses of T-cells proposed for treatment stems not only from our Phase I trial but also from our studies quantitating doses of unselected T-cells required to induce GvHD and the doses of EBV-CTLs required to induce regressions of EBV lymphomas following allogeneic HCT. Our studies of the incidence of GvHD in recipients of T-cell depleted matched or 1 allele mismatched HCT suggest that a dose of  $\geq 10^5$  allo cytotoxic T-cell (CTLp)/kg, as quantitated by limiting dilution analyses, represents the threshold dose for development of grade II or greater GvHD (44). In-vitro sensitization of T-cells against CMV or EBV for a period of 28 days results in preferential proliferation of antigen specific T-cells with simultaneous depletion of alloreactive T-cells by at least 100 fold (45). Therefore, in the doses of adimlecleucel proposed for treatment in this trial ( $1 \times 10^6$ /kg x 3 T-cells /kg), the doses of potentially alloreactive T-cells administered would be estimated to be below the GvHD threshold. In practice, the CMVpp65CTL after this culture period do not contain detectable allocytotoxic activity against patient or fully allogeneic PHA blasts. Indeed, this lack of alloreactivity is a release criterion that must be met to use the cells for treatment.

Our clinical experience also confirms this. In our Phase I trial of CMVpp65CTL, no patient developed GvHD. Similarly, none of the 19 patients with EBV lymphomas in our initial study developed GvHD when treated with transplant donor derived EBV specific T-cells sensitized for 4 weeks with irradiated autologous EBV BLCLs at doses ranging from  $15-150 \times 10^5$  T-cells/kg (29). Rooney et al (27), also observed no cases of GvHD among 39 patients treated prophylactically with transplant donor derived EBV specific T-cells generated by a similar technique over a dose range of  $3.3 - 33 \times 10^5$  T-cells /kg. Similarly, in our studies of HCT patients treated with third party virus-specific T-cells for either rituximab refractory EBV lymphoma (N=33) or persistent CMV infection (N=65), a total of 4 patients developed de novo GvHD or exacerbation of existing GvHD for 100 days.

Thus, based on our own experience, as well as data from published series, the risk of GvHD is expected to be very low, and the doses of infused adimlecleucel will provide enough numbers of CMV reactive T-cells to produce effective responses against CMV infection.

## 5.0 THERAPEUTIC/DIAGNOSTIC AGENTS

### 5.1 Donors of CMV-Specific T-cells

The CMV-specific T-cell lines to be used for treatment in this protocol and to be maintained cryopreserved under GMP conditions in the Adoptive Immune Cell Therapy Facility at MSKCC, will be derived from the groups listed below:

1. Normal, HLA typed, CMV-seropositive related and unrelated hematopoietic cell transplant donors who have consented to provide blood or blood white cells to make CMV-specific T-cells for treatment of CMV in the recipient of their transplant and have also specifically consented to the use of their CMV-specific T-cells for another patient, at such time as the transplant recipient is no longer at risk for this complication.

2. Normal, healthy HLA typed, CMV-seropositive volunteer blood donors who consent to provide blood or blood white cells to make CMV-specific T-cells for treatment of CMV infections in transplant recipients whose T cells may add to the HLA diversity of the T cells available in the Adoptive Immune Cell Therapy Bank.

Normal donors are evaluated for evidence of prior sensitization to CMV by CMV serology. Adequate health for donation will be ascertained according to institutional (related donor), NMDP (unrelated donor) or AABB (normal blood donors) guidelines. They are also typed for HLA A, B, C, DR and DQ.

Clinical studies for donors are obtained within 1 week of blood donation and include medical history and physical exam, CBC with differential and platelet count. Results of tests must be within a range that would not preclude donating blood or undergoing leukapheresis.

Serologic testing for transmissible diseases is performed as per each department's guidelines or at the discretion of the treating attending.

For prospective transplant donors, an informed consent will be obtained and up to 2 blood samples will be collected: Consenting volunteer blood donors will be requested to provide a leukapheresis.

#### Generation of Antigen Presenting cells (Dendritic cells and EBV BLCL ) and Peptide Loading of APCs

The DCs used for T-cell sensitization are generated from PBMCs isolated from blood leucocytes by Ficoll-Hypaque gradient separation and enriched for monocytes by adherence to plastic sterile tissue culture plates or by positive selection with CD14 clinical grade microbeads (miltenyi) if the frozen/thawed PBMC is used. The monocytes are then re-suspended at a concentration of  $1 \times 10^6$  cells/ml in RPMI supplemented with 1% heat inactivated autologous serum (if available) or prescreened heat inactivated human AB serum (Gemini) clinical grade GMCSF (2000 IU/ml) and *interleukin-4* (1000 IU/ml). The cultures are supplemented with these cytokines on days 2 and 4 in fresh medium as indicated by cell growth. On days 5 or 6, 5 ng/ml of *TNF $\alpha$* , 2.5 mg/ml of *IL-1 $\beta$* , 75  $\mu$ g/ml of *IL-6* and 0.5 $\mu$ g/ml *PGE-2* are added for 48 hours to induce maturation of dendritic cells. Thereafter, the dendritic cells are washed, adjusted to a concentration of  $1 \times 10^6$ /ml, and loaded with the pool (25 $\mu$ g complete pool/ml) of overlapping CMV-pp65 synthetic peptides (Invitrogen, Boston Massachusetts) in serum free medium at 37°C for 3 hours and used for T-cell sensitization as described below.

EBV transformed B cells are generated as described previously (46), adjusted to a concentration of  $1 \times 10^6$ /ml, and loaded with 25 $\mu$ g CMVpp65 peptide pool/ml in serum free medium at 37°C for 3 hours and used for T-cell sensitization.

#### Generation of CMVpp65 Specific T-cells (adimleculecel)

T-cells will be generated as described in published reports and detailed in the appendices (45). Briefly, CD3+ enriched T-cell fractions are initially isolated by ficoll-hypaque gradient separation of peripheral blood leucocytes. Thereafter, monocytes are depleted by adherence to the plastic tissue culture flasks or by immunoabsorption using clinical grade CD14 immunomagnetic microbeads (Miltenyi Biotechnology, GmbH, Gladbeck, Germany) if done from frozen/thawed PBMC. The CD56 $^+$  NK $^+$  cells and B cells are then removed by immunoabsorption to immunomagnetic beads coated with clinical grade mouse monoclonal antibody specific for CD56 and CD19 respectively (CliniMACS CD56 reagent, Miltenyi Biotechnology, GmbH, Gladbeck, Germany). Aliquots of  $1 \times 10^6$  T-cells /ml will then

be stimulated with  $0.5 \times 10^5$ /ml autologous irradiated monocyte- derived DC or with EBV BLCL previously loaded with a pool of 138 synthetic overlapping pentadecapeptides spanning the sequence of CMV pp65. The stimulated T-cells will then be cultured in modified Yssel's medium supplemented with 5% pre-screened heat inactivated human AB serum in sterile flasks at 37°C, with 5% CO2 in air. The culture will be re-stimulated with the peptide loaded DCs or EBV BLCL at an effector to target ratio of 10:1 at 7 day intervals for 21-28 days. Clinical grade IL-2 (Chiron) will be added to a concentration of 10-80 IU/ml every 3 days, beginning on day 7 and IL-15 weekly at the dose of 10ng/ml (stimulation with DCs does not potentiate significant expansion of T-cells. The earlier initiation of cytokine stimulation at higher doses permits generation of higher numbers of T-cells to meet the dose requirements in the protocol. IL-15 has been described as a potent stimulator of T-cell expansion in-vitro. After 21-28 days in culture, the T-cells will be harvested, counted and tested for potency, specificity and lack of alloreactivity, microbiological sterility, and for levels of endotoxin (confer appended Standard operating procedures). If a sufficient number of T-cells is obtained, the T-cells will then be aliquoted into sterile vials in calculated doses tested as detailed below and cryopreserved for subsequent administration to the recipient of the donor's HCT or for a third party recipient if consented, for treatment of CMV infection or persistent viremia. If additional numbers of T-cells are required, the pre-generated adimleculel will be further expanded using OKT3, IL2 and autologous feeders as described in our currently active clinical trial using WT1 CTLs (IRB#07-055)

The dendritic cells, EBV BLCL and T-cell lines will be generated in the designated Adoptive Immune Cell Therapy facility of MSKCC under controlled GMP conditions.

#### Characterization of CMVpp65-specific T-cells (adimleculel)

Depending on their growth, T-cell cultures will be evaluated after 21-28 days of culture for the proportion of CD4+ and CD8+ T-cells and content of CD3- CD56+ NK cells and CD20+ Cells. They will also be evaluated for their content of CMVpp65 specific IFNy+ CD8+/CD4+ T-cells in response to short secondary stimulation with autologous PBMC loaded with CMVpp65 peptide pool. Specificity will also be ascertained by demonstration of the absence of significant responses to secondary stimulation with unloaded donor and recipient PHA blasts, as well as fully allogeneic EBV BLCL. The matrix of pentadecapeptide subpools approach described by our laboratory (34) will be used to identify specific epitopes inducing IFNy responses with the CD8+ and CD4+ T-cells. The T-cells will also be tested for their capacity to lyse both CMVpp65 peptide loaded targets and CMV-infected donor and patient PHA blasts. In addition, a panel of single HLA matched EBV BLCL, both loaded and unloaded with CMVpp65, will be used as targets for in-vitro cytotoxicity to determine the HLA restriction of the CMV specific T-cells generated (43, 45).

T-cell cultures providing the required dose of adimleculel and lacking more than background responses to unloaded donor and recipient cells will be cryopreserved for use in adoptive immunotherapy. Immediately prior to cryopreservation, T-cells will be tested by standard techniques for microbiological sterility, absence of mycoplasma and absence or acceptably low levels of endotoxin (confer appended standard operating procedures). T-cells will be considered acceptable for administration if:

1. They are microbiologically sterile, free of mycoplasma and contain  $\leq 5$  EU of endotoxin/kg recipient weight/dose/hour infusion of T-cell culture
2. The T-cells can specifically lyse CMV-peptide loaded donor and /or host APCs.

3. The T-cells do not lyse unmodified PHA blasts of the transplant recipient or, if not evaluable, PHA blasts from a fully allogeneic blood donor above levels of cytotoxicity detected against autologous PHA blasts.
4. Whenever possible, aliquots of these T-cells will be saved to determine the T-cell receptor V $\beta$  repertoire of T-cells reactive against specific epitopes.

Unused T-cells will be maintained cryopreserved under GMP conditions in the Adoptive Immune Cell Therapy facility at MSKCC after the patient's transplant, after which they will be used (i) as 3rd party CMV or EBV specific T-cells if consented to by the donor, for the treatment of other patients such as recipients of cord blood HCT, or marrow or PBSC HCT from seronegative donors, or donors who are either not available or did not consent to provide leukocytes for generation of CMV-specific CTL.

## **6.0 CRITERIA FOR SUBJECT ELIGIBILITY**

Patients eligible for this trial will be 1) consenting recipients of related or unrelated alloHCT, SOT recipients, or patients with HIV or other immunocompromised states or immune competent subjects who require therapy who 2) have an active CMV infection or persistent CMV viremia despite 2 weeks of antiviral therapy or who cannot be maintained on antiviral agents due to therapy related toxicity, and 3 do not have CMV-specific T-cells from the donor of their HCT available.

### **6.1 Subject Inclusion and Exclusion Criteria**

#### **6.1.1 Patient Inclusion Criteria**

1. Each patient must satisfy at least one of the following criteria:
  - a. The patient has a clinically documented condition associated with CMV (e.g. interstitial pneumonia, hepatitis, retinitis, encephalitis, colitis)
  - b. The patient has microbiological evidence of CMV viremia or tissue invasion as attested by viral culture, or detection of levels of CMV DNA in the blood or body fluids consistent with CMV infection
2. Patient must also satisfy at least one of the following criteria:
  - a. CMV disease is persistent despite  $\geq$  2 weeks of antiviral therapy or progressing
  - c. CMV viremia is persistent or increasing (determined by quantitation of blood CMV DNA) despite  $\geq$  2 weeks of antiviral therapy
  - d. A genetic mutation associated with antiviral drug resistance is present
  - b. Unable to continue antiviral drugs due to drug-associated toxicity
3. CMV infections are life threatening, and may involve multiple organ systems such as the lungs, liver, gastrointestinal tract, hematopoietic and central nervous systems. Antiviral drugs used for treatment may also compromise renal and hematopoietic function. Therefore, dysfunctions of these organs will not affect eligibility for this protocol (e.g. Alanine aminotransferase (ALT) and aspartate aminotransferase (AST)  $< 3\times$  the upper limit of normal (ULN) and total bilirubin  $< 2.5\times$ ULN unless caused by CMV)

4. Patients must meet the following clinical criteria:
  - a. Stable blood pressure and circulation, not requiring pressor support
  - b. Evidence of adequate cardiac function as demonstrated clinically and/or by echocardiography
  - c. A life expectancy of at least 3 weeks, even if requiring artificial ventilation
  - d. There are no age restrictions
5. Patient must also satisfy the following criteria:
  - a. For subjects who received an alloHCT, the underlying disease for which the alloHCT was performed is in morphologic remission
  - b. Availability of appropriate, HLA partially-matched and restricted, adimleculeucel product
  - c. Subject or subject's representative is willing and able to provide written informed consent

#### **6.1.3 Patient Exclusion Criteria**

1. Patients requiring high doses of glucocorticosteroids ( $\geq 0.5$  mg/kg prednisone or its equivalent)
2. Receiving concomitant investigational therapy (co-enrollment in a non-interventional study or a study for follow-up or sample collection is permitted)
3. Need for high or moderate dose methotrexate or extracorporeal photophoresis for disease control or treatment of active GvHD. Other antimetabolite or T cell directed agents such as azathioprine, tocilizumab or ruxolitinib for control of rejection, autoimmunity or GvHD are allowed but should be discussed with the PI.
4. Antithymocyte globulin or similar anti-T cell antibody therapy  $\leq 4$  weeks prior to the first dose of adimleculeucel
5. Need for vasopressor or ventilator support
6. Pregnancy
7. Female of childbearing potential or male with a female partner of childbearing potential unwilling to use a highly effective method of contraception
8. Patients with other conditions not related to CMV infection (e.g. uncontrolled bacterial sepsis, other oral infections or invasive fungal infection) which are also life-threatening and which would preclude evaluation of the effects of a T-cell infusion
9. Inability to comply with study procedures
10. Patients who are moribund

## **7.0 RECRUITMENT PLAN**

### **7.1 Recruitment Procedures**

#### **7.1.1 Patient Recruitment**

Eligible patients undergoing allogeneic HCT who are eligible, will be recruited to this trial under the supervision of the allogeneic marrow transplant services in Medicine and Pediatrics.

Eligible patients will be interviewed prior to enrollment on this study, to explain the purpose and the involved treatments and procedures. The risks and benefits of participating in the trial and receiving third-party adimleculeucel infusions will be presented and discussed. These explanatory discussions will include a participating investigator and the patient. A non-participating family member or research nurse should be involved whenever possible.

## 7.2 Inclusion of Women and Minorities

Memorial Sloan-Kettering Cancer Center has filed form HHS 441 (re: Civil Rights), form HHS 641 (handicapped individuals), and form 639-A (re: Sex Discrimination). In selecting patients for study in the projects proposed in this protocol, we have taken due notice of NIH/ADAMHA policies concerning inclusion of women and minorities in clinical research populations. We expect that the study population will be fully representative of the range of patients seen at Memorial Hospital without exclusion as to age, gender, or ethnic background. Based on a January 1, 2001- December 2005 analysis of patient populations on allogeneic transplant protocols at this Center, the racial distributions were 24% African American, Hispanic or Asian, and 76% Caucasian. The gender distribution was 41% female and 59% male. The protocol is open to all patients irrespective of gender or ethnic background. The population of patients transplanted reflects the distribution of the patients in our tri-state referral area. However, it is anticipated that the distribution of patients by race and ethnicity will be the same for patients receiving marrow or PBSC transplants, but that a higher proportion of individuals from minority racial groups will be accrued to the cord blood transplant protocols, both because of the greater HLA disparity permissible and the concerted efforts of these banks to obtain donor units from populations underrepresented in the NMDP. Given the highly specific patient population that is subject/eligible for this treatment, the trial will be registered under clinical trials.gov to enable other transplant centers to review and refer patients for treatment. No other specific outreach efforts are planned for accrual.

Pregnant women are excluded from this study. There are no age restrictions for this study, and eligible children will be enrolled if appropriate consents are obtained from parents and /or guardians.

## 8.0 PRETREATMENT EVALUATION

Prior to adimleculeucel infusion, eligible and consenting patients will be clinically assessed for their general condition and for extent of CMV infection. Tests/exams will be obtained within 28 days of the first infusion. Tests easily repeated (e.g. blood work and chest x-ray) will preferably be performed within 3 days of infusion. Certain tests may be omitted at the discretion of the treating physician:

- Clinical history
- Physical examination ECHO and/or EKG, if clinically indicated
- CBC with differential
- Comprehensive Panel
- Cultures of affected body fluids or tissues will be obtained whenever possible

- CMV viremia will be assessed by quantitation of CMV DNA in the blood by real-time quantitation PCR
- Chest x-ray (not necessary if CT scan is done)
- GvHD assessment
- Pregnancy test for women of childbearing potential
- Review of concomitant medications:
  - CMV Anti-viral drugs: Foscarnet, Ganciclovir, Cidofovir, Valganciclovir, CytoGam, Brincidofovir, Maribavir, Leflunomide
  - Other CMV treatments: Donor Derived cells
  - Antithymocyte globulin or similar anti-T cell antibody therapy (e.g., OKT3), moderate or high dose methotrexate, or extracorporeal photopheresis.
  - Immunosuppressants: Tacrolimus, Cyclosporine, Sirolimus, MMF, Budesonide, Hydrocortisone, Methylprednisolone/Prednisone (at allowed doses). In addition, azathioprine, ruxolitinib and tocolizumab are allowed if not being used for active GvHD or solid organ rejection and must be discussed with the PI prior to enrollment on study.
- Ophthalmologic exam for CMV retinitis, if clinically indicated
- Colonoscopy for CMV colitis, if clinically indicated
- CT scan, if clinically indicated
- Lymphocyte immunophenotype (BMT short panel) and T cell responses to PHA and CandidaAlbicans, if clinically indicated

In addition, T cell responses to CMV will be evaluated in [name] laboratory by:

- Assessment of T cell proliferation in response to CMV antigens and lymphocyte characterization by flow cytometric phenotyping
- Quantitation of T cells generating IFN $\gamma$  in response to stimulation with a pool of CMV pentadecapeptides
- Quantitation of T cells binding CMV peptide by tetramer analysis in patients expressing HLA alleles for which there are tetramers available
- Analysis of TCR V $\beta$  repertoire

## 9.0 TREATMENT/INTERVENTION PLAN

This is a single institution phase II trial designed to assess the therapeutic activity of third-party donor-derived CMVpp65 specific T-cells (adimleculecel) for the treatment of CMV infection or persistent CMV viremia after allogeneic hematopoietic stem cell transplantation. The T-cells will be generated from healthy, CMV seropositive donors by sensitization in vitro with autologous antigen presenting cells, loaded with a pool of overlapping synthetic peptides spanning the sequence of CMV protein pp65.

### 9.1 Treatment with adimleculecel

This study will enroll subjects regardless of the underlying susceptibility to CMV, including alloHCT, SOT, human immunodeficiency virus, other immunocompromised states, and immune competent subjects who require therapy. Subjects must have active CMV viremia or disease for  $\geq 2$  weeks

despite treatment with antiviral therapy or must be intolerant to antiviral therapy due to treatment-related toxicity or comorbidities such as renal insufficiency or myelosuppression.

Subjects will receive adimleculeucel from cell lines generated from normal alloHCT donors or healthy donors, specifically consented for this purpose, based on having a partial match of  $\geq 2$  HLA alleles shared between the donor and the subject including the HLA restricting allele of the adimleculeucel cell product.

Adimleculeucel will be administered in cycles lasting 5 weeks (35 days). During each cycle, subjects will receive IV adimleculeucel at a dose of  $1 \times 10^6$  cells/kg (with an acceptable range of 0.8 –  $1.2 \times 10^6$  cells/kg) for 3 weeks or total dosing of  $2.4 - 3.6 \times 10^6$  cells/kg per cycle on days 0, 7, and 14. Tests quantitating CMV viremia by CMV DNA copies per milliliter of blood should be obtained weekly for the first 8 weeks post-initial infusion with CMV-specific T-cells, and then at approximately monthly intervals until 6 months post infusion.

Additional 3 week courses of adimleculeucel may be administered if patients have ongoing disease and/or levels of CMV DNA in blood are still detectable. These secondary courses will usually employ T-cells from the same third party donor. However, adimleculeucel derived from an alternate third party donor's CMV pp65-specific T-cells may be used if no further cells from the same donor are available or for patients with stable or progressive CMV infection refractory to antiviral drugs, since infusion of virus specific T-cells from a secondary donor specific for a different CMV peptide and restricted by the same or an alternate HLA allele shared by the recipient has, in several cases, induced durable regression of disease (23).

Subjects will generally be treated for a maximum of 2 cycles, though subjects achieving PR by the end of Cycle 2 may receive a third cycle. Subjects with PD at the end of Cycle 1 or later, or who experience unacceptable toxicity, will be offered Switch Therapy if appropriate.

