#### SUMMARY OF ACTIONS TO BE TAKEN ON THE DISEASE RESPONSE WITH EACH CYCLE

Response	Action	Notes
Complete Response (CR)	-	-
Partial Response (PR) / Stable Disease (SD)	If available, administer another cycle of adimleculeucel from the same cell line and reassess	Maximal response is a PR after 3 consecutive PR responses; after maximal response (3 cycles resulting in PRs), then observe
Stable Disease (SD)	If SD is the first Cycle response, administer the same adimleculeucel cell line for the next cycle and reassess; if SD is the second Cycle response, administer a different adimleculeucel cell line from a different donor (Switch Therapy) for the next cycle and reassess	If the subject has SD after 2 cycles of the same adimleculeucel cell line, a different adimleculeucel cell line may be administered (Switch Therapy)

Progressive Disease (PD)	Subsequent Cycles of adimleculecel with different restricting HLA alleles from a different donor(Switch Therapy)	If Switch Therapy results in CR/PR/ SD continue with subsequent cycle of adimleculecel from the same donor, then observe. If Switch Therapy results in PD, discontinue therapy.
--------------------------	--	--

All subjects receiving antiviral drugs can remain at their current dose during the adimleculecel treatment period. Subjects may also continue treatment with rapamycin and calcineurin inhibitors. Corticosteroid doses should be reduced to the lowest acceptable dose; adimleculecel has not been administered with prednisone-equivalent daily doses > 0.5 mg/kg.

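### Section 4.2, the Section 9.1 text and the action table disagree on re-treatment after a second SD, after Switch Therapy and after progression

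*Combined protocol and SAP*

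**What the plan says.** Three places govern further cycles.

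- **Section 4.2 (Intervention).** Additional courses "may be administered if levels of CMV DNA in blood are still detectable despite disease stabilization or improvement".
- **Section 9.1, text.** Additional courses "may be administered if patients have ongoing disease and/or levels of CMV DNA in blood are still detectable". An alternate donor's cells may be used when the first donor's supply is exhausted, or "for patients with stable or progressive CMV infection refractory to antiviral drugs". The number of cycles is then limited: "Subjects will generally be treated for a maximum of 2 cycles". The only extension attached to that sentence is a third cycle for patients in PR when Cycle 2 ends. The next sentence offers Switch Therapy, where appropriate, to patients with PD after Cycle 1 or any later cycle, or with unacceptable toxicity.
- **Section 9.1, action table.** The row labelled "Partial Response (PR) / Stable Disease (SD" calls for another cycle from the same line, if available, and stops after three PRs in a row. A separate SD row repeats the same line after a first SD, but "if SD is the second Cycle response, administer a different" line for the next cycle. The PD row gives Switch Therapy. If the switch yields CR, PR or SD, its note adds one more cycle from that donor and then observation; if the switch yields PD, treatment ends.

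Section 12 scores response after each cycle and records best response over the whole course as a separate item. Section 14 counts CR or PR as defined in Section 12 and does not say which of the two is meant.

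**The concern.** A re-treatment rule in a single-arm trial is part of the intervention being tested. If the same patient gets two, three or four cycles depending on which paragraph the treating physician reads, the regimen is not fully defined.

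Two things are at stake. The first is cumulative T-cell exposure: the risk of inducing or worsening GvHD is a primary objective in Section 2.0, and exposure rises with each cycle. The second is conditional: if a response in any cycle counts toward the primary endpoint, each extra cycle given to a non-responder is another chance to become a responder.

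**Working it through.** **1. Follow each response sequence through the two parts of Section 9.1.**

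| Responses so far | Section 9.1 text | Action table |
|---|---|---|
| SD, SD | No third cycle named | SD row: Cycle 3, different line. Joint PR/SD row: Cycle 3, same line. A Cycle 4 follows if the switch works and the PD-row note is applied to it |
| PD, then SD or CR on the switch line | Cycle 2 is the switch; no third cycle named | Cycle 3 from the switch donor, then observe |
| SD, PD, then SD on the switch line | Cycle 3 is the offered switch; nothing further named | Cycle 4 from the switch donor, then observe |
| PR, PR, PR | Three cycles | Three cycles, then observe |

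The last row agrees; the others do not. After a second SD the table also disagrees with itself, because its two SD entries give different products for the same state. Within the SD row, the action column directs the switch and the note only permits it.

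**2. Overall maximum.** The table gives none. PR, PR, PD leads to a switch as Cycle 4, which the 9.1 text also allows, and the table then adds Cycle 5 if the switch gives CR, PR or SD. On a literal reading, PR, PR, SD repeated never reaches three PRs in a row. The SD row speaks only of first- and second-cycle responses, so the joint row keeps repeating the line.

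**3. Who qualifies.** Section 4.2 covers patients "if levels of CMV DNA in blood are still detectable despite disease stabilization or improvement". A patient with PD after Cycle 1 does not meet that description. Section 9.1 covers patients "if patients have ongoing disease and/or levels of CMV DNA in blood are still detectable", and both its text and the table re-treat PD by switching. For that patient the Section 4.2 wording provides no further course, while 9.1 and the table provide at least one.

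**4. Exposure.** Inputs from Sections 4.2 and 9.1: 0.8 to 1.2 x 10^6 cells/kg per dose, three doses per cycle.

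- One cycle: 3 x 0.8 = 2.4 to 3 x 1.2 = 3.6 (x 10^6/kg). This reproduces the protocol's own per-cycle range.
- Two cycles: 4.8 to 7.2
- Three cycles: 7.2 to 10.8
- Four cycles: 9.6 to 14.4

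For SD then SD, the choice of passage changes cumulative exposure by 2.4 to 3.6 x 10^6/kg, half as much again as two cycles.

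**5. The efficacy test (sensitivity only).** Section 14 continues with at least 16 responders in 36 and declares activity with at least 33 in 69. The exact probability of declaring activity is

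P(p) = sum over x = 16 to 36 of Bin(x; 36, p) x Pr[Bin(33, p) >= max(0, 33 - x)].

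This gives 0.0999 at p = 0.40 and 0.900 at p = 0.56, so the stated error rate and power reproduce.

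Now assume that best response is counted, that 0.40 refers to the shorter course, and that extra cycles convert a share c of non-responders. Then p = 0.40 + 0.60c:

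| c | p | P(declare active) |
|---|---|---|
| 0 | 0.400 | 0.100 |
| 3% | 0.418 | 0.163 |
| 5% | 0.430 | 0.217 |
| 10% | 0.460 | 0.384 |

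The documents give no value for c and support none of these assumptions directly.

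**The case against.** Much of the text is permissive. The two-cycle limit is qualified by *generally*, further courses are allowed rather than required, and the switch is subject to being appropriate. Section 10.1.1 and the schedule footnotes foresee patients with more than two cycles. Some variation is therefore intended and would remain after any rewording. That stands, but permissive wording cannot reconcile two table rows that give different products for the same state.

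Several stronger readings are tempting, and the documents do not support them:

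- *Section 9.1 bars treating PD beyond two cycles.* It does not. Its offer of Switch Therapy extends to PD after any cycle, and text and table agree on the switch itself. The disagreement is over the additional cycle after the switch.
- *Section 4.2 forbids re-treating PD.* It states a condition for further courses without calling it exclusive. It is narrower than Section 9.1 and needs aligning, but it is not a prohibition.
- *SD is contradictory throughout the table.* After a first SD both rows repeat the same line. They part only at the second.
- *About 40% of patients, or 28 of 69, meet a conflict.* A reader might take this from Section 3.0, where 3 of 20 earlier third-party recipients had SD and 5 had PD. Those counts are not tied to a cycle, and SD or PD after Cycle 1 does not by itself create a conflict within Section 9.1.
- *Three cycles is itself outside the plan.* Section 9.1 allows three for PR, so 10.8 x 10^6/kg is already foreseen for some patients. The issue is which patients reach it.

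**Conclusion.** The re-treatment rules conflict at three points: (a) SD after Cycle 2, where the text and two table rows give three different answers; (b) the cycle added after a successful switch, which can exceed the Section 9.1 maximum in a table with no overall limit; and (c) Section 4.2, whose condition leaves out the progressive disease that Section 9.1 and the table re-treat. At point (a) the rule cannot be followed as written.

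The size that can be stated is exposure for the SD-then-SD patient: up to 7.2 x 10^6 cells/kg if treatment stops at two cycles, up to 10.8 x 10^6 if the third is given. How many patients this concerns cannot be derived from the documents.

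A reader might also infer that the type 1 error is inflated. The documents do not establish that. It would require that Section 14 counts best response, which it does not say, and that extra cycles convert non-responders at some rate, which is not given. Extra cycles for patients already in PR add exposure but no new responders; only re-treated SD and PD patients could add them. The Section 14 design figures themselves are correct.

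**What to change.** Reconcile Section 4.2, the Section 9.1 text and the action table into one rule. For each response category and cycle number it should state whether a further cycle is given, from which line, and the overall maximum including cycles after Switch Therapy. List SD in one row only, say whether the post-switch note applies when the switch followed SD, and make the action and note columns agree on whether the switch is directed or permitted. Where discretion is intended, say so in that rule. Which rule applies is for the sponsor and investigators to decide.

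The cost is protocol wording only. The sample size, the stopping boundaries and the visit schedule need not change.
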